7.2 Serious Adverse Events (SAEs)

7.2.1 Definitions

The SAE definition and reporting requirements are in accordance with the International Conference of Harmonisation (ICH) Guideline for Clinical Safety Data Management: Definitions and Standards for Expedited Reporting, Topic E2A.

An SAE is defined as any untoward medical occurrence that at any dose:

- Result in death.
- Is immediately life-threatening (i.e., in the opinion of the Investigator, the AE places the subject at immediate risk of death; it does not include an event that, had it occurred in a more severe form, might have caused death).
- Requires inpatient hospitalization or results in prolongation of an existing hospitalization.
 - Note: While most hospitalizations necessitate reporting of an SAE, some hospitalizations do not require SAE reporting, as follows: elective or previously scheduled surgeries or procedures for pre-existing conditions that have not worsened after initiation of treatment (e.g., a previously scheduled ventral hernia repair); pre-specified study hospitalizations for observation; or events that result in hospital stays of fewer than 24 hours and that do not require admission (e.g., an ER visit for hematuria that results in a diagnosis of cystitis and discharge home on oral antibiotics). SAEs must, however, be reported for any surgical complication resulting in prolongation of the hospitalization.
- Results in significant incapacity or substantial disruption of the ability to conduct normal life functions.
- Is a congenital anomaly or birth defect.
- Is an important medical event (IME).
 - Note: The term "important medical event" refers to an event that, based upon
 appropriate medical judgment, may not be immediately life-threatening or result in
 death or hospitalization, but may jeopardize the subject or require medical or surgical
 intervention to prevent one of the outcomes listed above. Examples of IMEs include

intensive treatment in an emergency room or at home for allergic bronchospasm; blood dyscrasias, or convulsions that do not result in hospitalization; or development of product dependency or product abuse.

 Suspected transmission of an infectious agent (eg, pathogenic or nonpathogenic) via the study drug is an SAE

7.2.2 SAEs Reporting

As soon as an Investigator becomes aware of an AE that meets the criteria for an SAE, the Investigator will document the SAE on an SAE Report Form in REDCap. SAEs must be recorded as Adverse Events using the electronic case report form in REDCap a clinical data management system (CTMS).

In addition, SAEs regardless of causal relationship, must be reported to Exelixis and BMS within one (1) business day of the Investigator's knowledge of the event by submitting a completed MedWatch report form.

Exelixis Reporting: The reports must be emailed to **[contact]** or faxed to **[contact]** with the below:

- Required Information:
 - Identity of Investigator
 - Site name
 - Subject identifiers
 - Drug name and dosage
 - Event description
 - o Event terms (i.e., as recorded in the electronic database)
 - Investigator's assessment of the relationship of the event to study treatment (Section 7.1)
 - The reason why the event is considered to be serious (i.e., the seriousness criteria)
 (Section 7.2.1)
- Recommended Information:
 - Medications or therapeutic measures used to treat the event
 - Action taken with the study treatment because of the event
 CONFIDENTIAL Cabozantinib + Nivolimab + Ipililumab Protocol Required Elements

- Outcome/resolution of the event
- Any additional SAE information

Note – Medical records should **not** be sent to Exelixis unless requested.

BMS Reporting: All SAEs that occur from first study treatment through 100 days of discontinuation of dosing must be reported to BMS Worldwide Safety, whether related or not related to study drug, including those thought to be associated with protocol-specified procedures (eg, a follow-up skin biopsy) within 24 hours \ 1 business day to comply with regulatory requirements. MedWatch 3500 form should be completed and submitted to BMS to report the SAEs.

Note: Please include the BMS Protocol number on the SAE form or on the cover sheet with the SAE form transmission. Medical Records should **not** be sent to BMS unless requested.

An SAE report should be completed for any event where doubt exists regarding its seriousness;

If the investigator believes that an SAE is not related to study drug, but is potentially related to the conditions of the study (such as withdrawal of previous therapy or a complication of a study procedure), the relationship should be specified in the narrative section of the SAE Report Form.

All SAEs must be reported by confirmed facsimile (fax) transmission or reported via electronic mail to the below email address and the BMS Protocol number must be included on the SAE form or on the cover sheet with the SAE form transmission

SAE Email Address: [contact]

SAE [contact]

If only limited information is initially available, follow-up reports are required. (Note: Follow-up SAE reports should include the same investigator term(s) initially reported.)

If an ongoing SAE changes in its intensity or relationship to study drug or if new information becomes available, a follow-up SAE report should be sent within 24 hours \ 1 Business Day to BMS using the same procedure used for transmitting the initial SAE report.

All SAEs should be followed to resolution or stabilization.

The causal relationship to study drug is determined by a physician and should be used to assess all adverse events (AE). The casual relationship can be one of the following:

- Related: There is a reasonable causal relationship between study drug administration and the AE.
- Not related: There is not a reasonable causal relationship between study drug administration and the AE.

The term "reasonable causal relationship" means there is evidence to suggest a causal relationship.

Adverse events can be spontaneously reported or elicited during open-ended questioning, examination, or evaluation of a subject. (In order to prevent reporting bias, subjects should not be questioned regarding the specific occurrence of one or more AEs.)

The Sponsor-Investigator will reconcile the clinical database AE cases (case level only) transmitted to BMS Global Pharmacovigilance ([contact]).

- The Investigator will request from BMS GPV&E, [contact] the SAE reconciliation report and include the BMS protocol number every 3 months and prior to data base lock or final data summary
- GPV&E will send the investigator the report to verify and confirm all AE and SAEs have been transmitted to BMS GPV&E.
- The data elements listed on the GPV&E reconciliation report will be used for case identification purposes. If the Investigator determines a case was not transmitted to BMS GPV&E, the case should be sent immediately to BMS ([contact]).

In addition to the Sponsor Investigator's responsibility to report events to their local HA, suspected serious adverse reactions (whether expected or unexpected) shall be reported by BMS to the relevant competent health authorities in all concerned countries according to local regulations (either as expedited and/or in aggregate reports).

In accordance with local regulations, BMS will notify sponsor investigators of all reported SAEs that are suspected (related to the investigational product) and unexpected (ie, not previously described in the IB). An event meeting these criteria is termed a Suspected, Unexpected Serious Adverse Reaction (SUSAR). Sponsor investigator notification of these events will be in the form of either a SUSAR Report or a Semi-Annual SUSAR Report.

- Other important findings which may be reported by BMS as an Expedited Safety Report (ESR) include: increased frequency of a clinically significant expected SAE, an SAE considered associated with study procedures that could modify the conduct of the study, lack of efficacy that poses significant hazard to study subjects, clinically significant safety finding from a nonclinical (eg, animal) study, important safety recommendations from a study data monitoring committee, or sponsor or BMS decision to end or temporarily halt a clinical study for safety reasons.
- Upon receiving an ESR from BMS, the investigator must review and retain the ESR with the IB.
 Where required by local regulations or when there is a central IRB/IEC for the study, the sponsor
 will submit the ESR to the appropriate IRB/IEC. The investigator and IRB/IEC will determine if the
 informed consent requires revision. The investigator should also comply with the IRB/IEC
 procedures for reporting any other safety information.

Although pregnancy and potential drug-induced liver injury (DILI), are not always serious by regulatory definition, however, these events must be reported within the SAEs timeline.

Any component of a study endpoint that is considered related to study therapy should be reported as an SAE (eg, death is an endpoint, if death occurred due to anaphylaxis, anaphylaxis must be reported).

NOTE: (PI determines if this information regarding hospitalizations are considered SAEs and should be included in the protocol.

The following hospitalizations are not considered SAEs in BMS clinical studies:

- a visit to the emergency room or other hospital department < 24 hours, that does not result in admission (unless considered an important medical or life-threatening event)
- elective surgery, planned prior to signing consent
- admissions as per protocol for a planned medical/surgical procedure
- routine health assessment requiring admission for baseline/trending of health status (eg, routine colonoscopy)
- Medical/surgical admission other than to remedy ill health and planned prior to entry into the study. Appropriate documentation is required in these cases.
- Admission encountered for another life circumstance that carries no bearing on health status and requires no medical/surgical intervention (eg, lack of housing, economic inadequacy, caregiver respite, family circumstances, administrative reason).
- Admission for administration of anticancer therapy in the absence of any other SAEs (applies to oncology protocols)

The Investigator will perform adequate due diligence with regard to obtaining follow-up information on incomplete reports. All follow-up information must be sent to Exelixis and BMS within one (1) business day of the Investigator's receipt of the new information.

SAEs that must be recorded on an SAE Reporting form include the following:

- SAEs that occur after initiation of study therapy and through 100 days after the date of the decision to permanently discontinue study treatment
- SAEs assessed as related to study treatment or study procedures, even if the SAE occurs more
 than 100 days after the date of the decision to permanently discontinue study treatment.

In all cases, the Investigator should continue to monitor the clinical situation and report all material facts relating to the progression or outcome of the SAE. Furthermore, the Investigator may be required to provide supplementary information as requested by Exelixis and/or BMS.

When reporting SAEs, the following additional points will be noted:

- When the diagnosis of an SAE is known or suspected, the Investigator will report the diagnosis or syndrome as the primary SAE term, rather than as signs or symptoms. Signs and symptoms may then be described in the event description.
- Death will not be reported as an SAE, but as an outcome of a specific SAE, unless the event
 preceding the death is unknown. Terms of "Unexplained Death" or "Death from unknown
 origin" may be used when the cause is unknown. In these circumstances the cause of death
 must be investigated, and the diagnosis amended when the etiology has been identified. If an
 autopsy was performed, the autopsy report should be provided.

7.2.3 Regulatory Reporting

The Investigator will assess the expectedness of each related SAE to the study treatment. The current cabozantinib Reference Safety Information (Appendix K of the most recent approved Investigator Brochure) will be used as the reference document for assessing the expectedness of the event with regard to cabozantinib.

The Investigator is responsible for reporting relevant SAEs to the relevant regulatory authorities, and participating investigators, in accordance with FDA regulations (21 Code of Federal Regulations [CFR] 312.32), ICH guidelines, European Clinical Trials Directive (Directive 2001/20/EC), and/or local regulatory requirements.

- These reports are to be filed utilizing the Form FDA 3500A (MedWatch Form)
- Exelixis Drug Safety group (or designee) will process and evaluate all SAEs as the reports are
 received. For each SAE received, Exelixis will make a determination as to whether the criteria for
 expedited reporting to relevant regulatory authorities have been met. Exelixis reserves the right
 to upgrade the Investigator assessment of an SAE based on Exelixis assessment.

- Institutions and Investigators shall promptly provide all information requested by Exelixis regarding all adverse events occurring during the conduct of the study.
- The Investigator is responsible for complying with all regulatory authority reporting requirements for the study that are applicable to the Principal Investigator of a clinical trial.
- The Investigator shall provide a copy of all responses to regulatory agency requests, periodic reports, and final study reports to Exelixis within one (1) business day of the submission.
- Exelixis will provide relevant product safety updates and notifications, as necessary. In the case
 of multi-center studies, it is the responsibility of the Principal Investigator to disseminate these
 updates to participating Investigators.
- Reporting of SAEs by the Investigator to his or her Institutional Review Board (IRB)/Ethics
 Committees (ECs) will be done in accordance with the standard operating procedures and
 policies of the IRB/EC. Adequate documentation must be maintained showing that the IRB/EC
 was properly notified.
- In the case of blinded studies, the treatment blind will be broken by the Principal Investigator
 and/or other necessary personnel prior to reporting an SAE that meets the criteria for
 expediting reporting to the Regulatory Authorities and to some central ECs. All personnel that
 are not involved in the unblinding and submission processes will remain blinded to the
 treatment assignment.

7.3 Adverse Events of Special Interest

Adverse events of special interest (AESIs) consist of immune-mediated AEs associated with ICIs, cases of potential DILI, and suspected transmission of an infectious agent by the study treatment. AECIs must be recorded as Adverse Events using the Events of Clinical Interest electronic case report form in REDCap's clinical data management system (CTMS).

AESIs will be reported to the Principal Investigator or designee using the SAE reporting form irrespective of whether the event is serious or nonserious; all AESIs must be reported within one (1) business day using the SAE process as described in Section 7.2.2.

Guidance for management of immune-mediated AEs is provided in the protocol (Section 5.4.2 - 5.4.3) and can also be found in the local prescribing information for each IO agent.

Adverse Events of Special Interest

Event

Cases of potential DILI that include an elevated ALT or AST in combination with either an elevated bilirubin or clinical jaundice, as defined by Hy's Law and based on the following observations:

Suspected transmission of an infectious agent by the study treatment, as defined below:

Any organism, virus, or infectious particle (e.g., prion protein transmitting transmissible spongiform encephalopathy), pathogenic or non-pathogenic, is considered an infectious agent. A transmission of an infectious agent may be suspected from clinical symptoms or laboratory findings that indicate an infection in a patient exposed to a medicinal product. This term applies only when a contamination of study treatment is suspected.

Pneumonitis

Colitis

Endocrinopathies: diabetes mellitus, pancreatitis, adrenal insufficiency, hyperthyroidism, and hypophysitis

Hepatitis, including AST or ALT > 10x ULN

Systemic lupus erythematosus

Neurological disorders: Guillain-Barré syndrome, myasthenic syndrome or myasthenia gravis, and meningoencephalitis

Events suggestive of hypersensitivity, infusion-related reactions, cytokine release syndrome, influenza-like illness, systemic inflammatory response syndrome, and systemic immune activation

Nephritis

Ocular toxicities (e.g., uveitis, retinitis)

Myositis

Myopathies, including rhabdomyolysis

≥ Grade 2 cardiac disorders (e.g., atrial fibrillation, myocarditis, pericarditis)

Vasculitis

7.3.1 General Information on Immune-Related Adverse Events

The immune-modulating properties of IO agents are able to undermine immunologic tolerance and generate a subset of AEs (called irAEs) with an autoimmmune inflammatory pathomechanism. Immune-related AEs may involve any organ or tissue²³. Most irAEs occur within the first 12 weeks of exposure to IOs but some may appear with a delayed onset. Diagnosis of irAEs should be based on exposure to an IO and a reasonable immune-based mechanism of the observed AE. Whenever possible, histologic examination or other immune-based diagnostic evaluations should be used to support the diagnosis. Other etiologic causes including AEs from tumor progression should be ruled out.

The spectrum of irAEs is wide and can be general or organ-specific. Examples of general irAEs in subjects treated with IOs are fatigue, fever, and chills. Organ-specific irAEs consist of dermatitis (rash, pruritus, vitiligo, oral mucositis, and gingivitis), enterocolitis (diarrhea with abdominal pain and clinical or radiological evidence of colonic inflammation), and endocrinopathies (pituitary, thyroid, adrenal, testes). Diagnosis of endocrine dysfunction is challenging with relatively unspecific symptoms. The following additional laboratory testing of the endocrine axes may be helpful: prolactin (pituitary-hypothalamic function), FT4 and TSH (pituitary-thyroid function), luteinizing hormone (LH) and follicle-stimulating hormone (FSH; pituitary-gonadal function), adrenocorticotropic hormone (ACTH) and cortisol (pituitary-adrenal function).

Additional organ-specific irAEs include hepatitis (AST/ALT increases, hepatomegaly, periportal edema, periportal lymphadenopathy, lymphocyte infiltration of periportal tissue and surrounding primary biliary ducts) and pneumonitis (acute interstitial pneumonia). Less frequent irAEs include neurologic syndromes (myasthenia gravis, Guillian-Barré syndrome, meningoencephalitis), ocular AEs (uveitis), renal AEs (interstitial nephritis), cardiac AEs (myocarditis), and pancreatic AEs (lipase increase).

7.4 Follow-up of Adverse Events

Nonserious AEs will be followed until 30 days after the date of the decision to discontinue study treatment. All SAEs and AESIs (regardless of seriousness) will be followed until 100 days after the date of decision to discontinue study treatment.

All AESIs (regardless of seriousness) and all related SAEs that are ongoing 100 days after the date of the decision to discontinue study, and AEs assessed as related that led to study treatment discontinuation that are ongoing 100 days after the date of the decision to discontinue study treatment, are to be followed until either:

- The AE has resolved.
- The AE has improved to Grade 2 or lower.
- The investigator determines that the event has become stable or irreversible.

7.5 Other Safety Considerations

7.5.1 Pregnancy/Lactation Exposure

Use of highly effective methods of contraception is very important during the study and must continue for 4 months after the last dose of cabozantinib and 3 months after the last dose of ipilimumab and 5 months after the last dose of nivolumab. If a subject becomes pregnant during the study, she will be taken off study treatment and will be followed through the end of her pregnancy and the infant should have follow up for at least 6 months after birth. If a female partner of a male subject becomes pregnant during the study, the Investigator will ask the pregnant female to consent to be followed through the end of her pregnancy and for the infant to be followed for at least 6 months after birth. Furthermore, male subjects must refrain from donating sperm in order to avoid transmission of study treatment in semen for the duration of study treatment and through 5 months after their last dose of study treatment. Both male and female subjects should seek advice and consider fertility preservation before receiving study treatment.

The Investigator must inform Exelixis/BMS of the pregnancy. The outcome of a pregnancy (for a subject or for the partner of a subject) and the medical condition of any resultant offspring must be reported to Exelixis/BMS. Any birth defect or congenital anomaly must be reported as an SAE, and any other untoward events occurring during the pregnancy must be reported as AEs or SAEs, as appropriate.

Females should not breastfeed while receiving study treatment and for up to 4 months from the last dose of cabozantinib and up to 5 months from the last dose of ipilimumab or nivolumab.

7.5.2 Medication Errors/Overdose

Medication error is defined as the administration of each study drug medication outside or above the established dosing regimens per the specific protocol. Any study medication overdose, misuse, abuse, or medication error (excluding missed doses) that results in an AE, even if it does not meet the definition of serious, requires reporting within one (1) business day to Exelixis and BMS.

In case of overdose, the Principal Investigator should be contacted promptly to discuss how to proceed. Any AEs that occur as a result of an overdose have to be treated according to clinical standard practice. Please refer to the cabozantinib Investigator Brochure for additional management recommendations regarding overdoses of cabozantinib.

8 STATISTICAL CONSIDERATIONS

Data and Statistical plan:

Recent clinical trials have demonstrated median PFS as high as 5 months with the combination of low dose ipilimumab (1 mg/kg IV every 3 weeks) with anti-PD-1 therapies in patients with anti-PD1 refractory cutaneous melanoma. In this clinical trial, we will use the 5 month mPFS as our benchmark. In order to show a 4 month improvement in mPFS over the 5 month historical data benchmark (with a power of 0.8 and a one-sided test given a type I error rate of 0.05), a total of 41 subjects would need to be enrolled.

This signal seeking pilot study will enroll 25 subjects at our site (single institution) in less than 2 years. If we find that this treatment combination results in a *mPFS of at least 8 months or an ORR of 45% or higher*, we will review these results with BMS and Exelixis and propose protocol and budget amendments to add 1-2 additional sites to expedite to a total of at least 41 subjects to be enrolled in a rapid timeframe.

Descriptive Statistics:

Descriptive statistics will be provided for all baseline, efficacy, and safety variables, as appropriate. Frequency counts and percentages will be provided for categorical data. Mean (standard deviation), median (interquartile range) will be calculated for continuous variables.

Statistical Analyses for Primary and Secondary Endpoints:

Primary endpoint: The progression-free survival (PFS) analyses will be performed considering the risk of dying from any cause before experiencing progression related events using the competing risk regression method²⁴. Cumulative incidence functions will be displayed and summarized for the median time to progression as well as percentage of patients without disease progression at 12, 18, and 24 months.

Secondary endpoints: ORR will be determined as the rate of the confirmed best overall response of either PR or CR per iRECIST. Using the efficacy evaluable analysis set, the Kaplan-Meier method will be used to estimate PFS, OS and DOR, and the summary statistics (e.g., 12-month survival and median CONFIDENTIAL - Cabozantinib + Nivolimab + Ipililumab Protocol Required Elements

Page 66 of 92

survival with 95% confidence intervals). DOR will be estimated only among responders (i.e. participants achieving at least once CR or PR). Data visualization tools such as waterfall plots (% change in tumor size) or swimmer plot (DOR) will be used to display the data.

Using the safety evaluable analysis set, the incidence of having Grade ≥ 3 AEs will be determined for study participants that received at least one dose of their assigned treatment. The point estimate and 95% confidence interval will be reported.

For correlative molecular profiling endpoint, paired t-test or Wilcoxon signed-rank test will be performed to evaluate tumor infiltrating immune cell profiling and gene expression changes between pre- and post-treatment.

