2 STUDY OBJECTIVES AND ENDPOINTS

Recent clinical trials have demonstrated median PFS as high as 5 months with the combination of low dose ipilimumab (1 mg/kg IV every 3 weeks) in combination with anti-PD-1 therapies in patients with anti-PD1 refractory cutaneous melanoma. As such, we will use the 5 month mPFS as the benchmark for the design of this clinical trial. In order to show a 4 month improvement in mPFS (with a power of 0.8 and a one-sided test given a type I error rate of 0.05), a total of 41 subjects would need to be enrolled. This signal seeking pilot study will initially enroll 25 subjects at our site (single institution) in less than 2 years. If this treatment combination results in a *mPFS of at least 8 months or an ORR of 45% or higher*, we will review these results with BMS and Exelixis and propose protocol and budget amendments to add 1-2 additional sites to expedite enrollment to a total of at least 41 subjects.

Primary Objective

The primary objective of this clinical trial is to evaluate the clinical efficacy and progression free survival of the triplet combination of ipilimumab + nivolumab + cabozantinib in patients with anti-PD-1/PD-L1 refractory metastatic cutaneous melanoma.

Secondary Objectives:

- Safety/Tolerability (CTCAE v5.0)
- Objective response rate (iRECIST)
- Overall survival
- Correlative translational studies (paired pre-treatment and day #15 on-treatment tumor biopsies for characterization of tumor infiltrating immune cell profiling and gene expression changes)

Primary endpoint:

Progression free survival will be defined as the time between the date of enrollment and the first date of documented progression (per iRECIST), as determined by the investigator, or death due to any cause, whichever occurs first. Cumulative incidence functions will be displayed and summarized for the median time to progression as well as percentage of patients without disease progression at 12, 18, and 24 months.

Secondary endpoints:

- 1. Objective response rate (iRECIST)
- 2. Duration of response
- 3. 6, 12 and 24 month progression free survival
- 4. 12 month overall survival
- 5. Incidence of grade ≥3 treatment related adverse events (CTCAE v5.0)
- 6. Correlative molecular profiling

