4.2 Treatment Period

During the Treatment Period subjects will receive treatment for up to 24 months or until either disease progression, the occurrence of unacceptable drug-related toxicity or for other reason(s) for subject withdrawal as described in Section 2.1. Subjects should be instructed to immediately inform the Investigator of any AEs. Subjects experiencing dizziness, sleepiness, or other symptoms that could influence alertness or coordination should be advised not to drive or operate other heavy machinery.

Abnormalities in clinical laboratory tests that lead to a change in subject management (e.g., dose delayed [withheld] or reduced, requirement for additional medication, treatment or monitoring) are considered clinically significant and should be documented. If laboratory values constitute part of an CONFIDENTIAL - Cabozantinib + Nivolimab + Ipililumab Protocol Required Elements

event that meets criteria defining it as serious, the event (and associated laboratory values) must be reported as an SAE.

Regular tumor assessments should be performed to determine if PD is present. Tumor assessments should continue on the protocol-defined schedule, relative to the date of first dose of study treatment, regardless of whether study treatment is given, reduced, held or discontinued. The same imaging modalities used at screening will be used for subsequent tumor assessments after first dose.

If the subject is unable to have a study assessment taken within the defined time window due to an event outside of his or her control (e.g., clinic closure, personal emergency, inclement weather, vacation), the assessment should be performed as close as possible to the required schedule.

The Treatment Period ends when a subject receives his or her last dose of study treatment; the subject then enters the Post-Treatment Period.

The following schedule of assessments applies to all subjects. More frequent assessments should be obtained if clinically indicated.

Study Assessments

Study Day/Visit Day	Cycles 1-4 (21 days) Day 1 (+/- 4 days)	Cycles 5 + Day 1 (+/- 4 days)	Instructions
Adverse Event Assessment	Х	Х	
Concomitant Medications	х	х	Review of prohibited medications prior to each study drug dosing
Physical Exam	X	Х	
Vital Signs	х	х	Weight, blood pressure, pulse, 02 saturation, respirations at each visit
ECOG Performance Status	x	x	
Questionnaire(s)	Х	Х	FACT-M (Version 4)
Cabozantinib 40 mg PO daily Continuous	х	х	

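### The stated 80% power and one-sided 5% error for median PFS of 9 v 5 months belong to no planned analysis, at 25 subjects or at 41

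*Combined protocol and SAP*

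**What the plan says.** Section 8 (Data and Statistical plan), like Section 2, takes a 5-month median PFS as the benchmark. To show a 4-month improvement, "with a power of 0.8 and a one-sided test given a type I error rate of 0.05", it says that "a total of 41 subjects would need to be enrolled".

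Both sections then commit to fewer. Section 2 has: "This signal seeking pilot study will initially enroll 25 subjects at our site (single institution) in less than 2 years". An increase to at least 41 is to be proposed to the two companies, as protocol and budget amendments, if the data show a "mPFS of at least 8 months or an ORR of 45% or higher".

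For the analysis of PFS, Section 8 names competing-risk regression with cumulative incidence displays as primary. As secondary, "the Kaplan-Meier method will be used to estimate PFS, OS and DOR", with 95% confidence intervals. Neither entry gives a null value, a test statistic or a criterion for success. The only significance tests that Section 8 names are the paired pre/post tests for the correlative endpoint.

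**The concern.** A power statement is a property of a particular test. Here the size text refers to a one-sided 5% test, but the analysis text contains no comparison of PFS with 5 months at either sample size. In a single-arm trial, competing-risk regression and cumulative incidence do not supply one.

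The trigger settles when expansion will be proposed. Nothing settles when PFS counts as better than the benchmark. If that is chosen after the data are seen, the 5% and the 80% protect nothing, and results can differ materially with the method picked. Scans 12 weeks apart add to this, because progression dates move to the next scan and a 5-month reference falls between two scans.

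**Working it through.** **Inputs.** From Sections 2 and 8: medians 5 and 9 (= 5 + 4) months, one-sided alpha 0.05, power 0.80, N = 41 or 25, accrual under 2 years. From Section 4.2: scans every 12 weeks ±1 week. Assumed: exponential PFS; accrual 24 months; further follow-up 0 to 12 months. z₀.₉₅ = 1.645, z₀.₈₀ = 0.842, and (1.645 + 0.842)² = 6.18.

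**1. Can 41 be reproduced?** PFS at 5 months is 0.50 under the null and 0.5^(5/9) = 0.680 under the alternative.
- Alternative variance only: 6.18 × 0.680 × 0.320 / 0.180² = 41.3.
- Null and alternative variances: [(1.645 × 0.5 + 0.842 × √(0.680 × 0.320)) / 0.180]² = 45.4.
- One-sample log-hazard test: 6.18 / ln(5/9)² = 17.9 events. With 24-month accrual plus 0, 6 or 12 months, N is about 33, 25 or 22.

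So 41 is reachable, but the documents do not say by which method.

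**2. Power at 25, true median 9, by test.**
- Exact binomial at 5 months, at least 18 of 25: alpha 0.022, power 0.43.
- Normal test of 5-month PFS: 0.57 (null and alternative variances) to 0.61 (alternative variance).
- Log-median test: Φ(√25 × ln 2 × ln 1.8 − 1.645) = 0.65.
- Log-hazard test, Φ(√D × ln 1.8 − 1.645): D = 13.6, 17.8 or 20.5 expected events (0, 6 or 12 months' follow-up) gives 0.70, 0.80 or 0.85.

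The range is 0.43 to 0.85. At 41 the same tests run from 0.69 (exact, at least 27 of 41) to 0.96 (log-hazard, +12 months).

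**3. Is the trigger the missing test?** With 25 exactly dated events, the observed median is at least 8 months when at least 13 subjects pass 8 months. The chance per subject is 0.5^(8/5) = 0.330 at a true median of 5 and 0.5^(8/9) = 0.540 at 9. The binomial tails are 0.038 and 0.66. The alternative ORR route adds to both by an amount the plan does not give. This is not a 5%/80% rule.

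**4. What if the planned interval were read against 5 months?** The plan states no such rule, so this is illustration only. A two-sided 95% limit is also one-sided 2.5%, not 5%. Simulated log-log Kaplan-Meier limits with exact dates give a lower limit above 5 months, at a true median of 9, in about 0.42 to 0.43 of trials at n = 25 and 0.55 to 0.56 at n = 41. At a true median of 5 and n = 25 the figure is 0.02.

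Now date progression at scans, aligned with the PFS origin. At n = 25 and a true median of 5:

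| Share of events dated exactly (assumed) | Lower limit above 5 months |
|---|---|
| 0% | 0.43 |
| 10% | 0.36 |
| 20% | 0.29 |
| 50% | 0.13 |

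If the benchmark was itself scan-dated (assumed underlying median 4.3), the first three become about 0.27, 0.21 and 0.16.

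**5. Expected precision at n = 25, true median 9.** The typical 95% interval is about 4.7 to 15 months with exact dates, and about 5.6 to 16.7 months on the scan grid.

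**6. A landmark test that fits the scan schedule.** Timed from first dose, the week-24 scan falls at latest on day 168 + 7 = 175, before 6 months (day 183). Week 24 is 5.52 months, so event-free probabilities are 0.5^(5.52/5) = 0.465 and 0.5^(5.52/9) = 0.654.
- At least 16 of 25: type I 0.060, power 0.645.
- At least 17 of 25: 0.025, 0.48.
- At least 25 of 41: 0.045, 0.78.

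Replacing 5.52/m by (5.52/m)^k gives Weibull PFS with the same median m. For k = 0.8 and 1.2, 17 of 25 has type I 0.030 and 0.021, power 0.37 and 0.59. For 25 of 41, type I is 0.054 and 0.037, power 0.65 and 0.87.

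**The case against.** The strongest reply is that the documents already describe a signal-seeking pilot. They attach 80% power to 41 in conditional terms, never to 25, and give an explicit go/no-go rule. The amendment needed to reach 41 could also name the test. Most of this stands. A reader might infer that the plan claims 80% power for 25 subjects; it does not. A reader might also infer that 25 is underpowered whatever is done; some one-sample tests reach 80 to 85% at 25 with 6 to 12 months' further follow-up.

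The reply does not close the gap. The current text already states alpha and power for a one-sided test, and no PFS test exists at 41 either. The go/no-go rule carries no error rate and has different operating characteristics.

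A second fair objection is that the false-positive figures in step 4 come from a decision rule the plan never states and from a share of exactly dated events that the documents do not give. Section 4.2 allows extra assessments when clinically indicated, which would raise that share. The figures are therefore a sensitivity range and not a property of the design.

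**Conclusion.** The point holds as a mismatch between the size statement and the analysis plan: the 80% and 5% describe no planned analysis at 25 or at 41. This follows from the text alone and needs no modelling.

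Two stronger readings are not supported. The figure 41 is not shown to be wrong, since a standard calculation gives 41.3; only its method is missing. And the plan cannot be said to carry an inflated false-positive rate, because it has no success rule to inflate.

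The sizes are conditional. Power at 25 runs from about 43% to 85% across tests and follow-up, under exponential PFS. If the Kaplan-Meier interval were read informally against 5 months, false positives at n = 25 could be roughly 13% to 43% with scan dating (50% down to 0% of events dated exactly), lower if the benchmark was scan-dated, and about 2% with exact dates. That spread is the reason to fix the rule, or disclaim one, in advance.

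**What to change.** In Section 8, with matching text in Section 2:

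1. State that the 25-subject stage is for estimation, that the 80%/5% statement does not apply to it, and that 8 months/45% is only a trigger to propose expansion.
2. Give the expected 95% interval for median PFS with its dating assumption: at n = 25 and a true median of 9, about 4.7 to 15 months with exact dates, or about 5.6 to 16.7 months with 12-week scan dating.
3. Tie the 80%/5% statement to one named one-sample PFS test at 41, with null value, method, time origin and follow-up. State how 41 was obtained, and restate the power if that test does not reach 80%.
4. Only if a test at 25 is wanted: one option is a single pre-specified test of 6-month PFS, since "6, 12 and 24 month progression free survival" is already a secondary endpoint. Time it from first dose, because PFS runs from enrolment ("Progression free survival will be defined as the time between the date of enrollment and the first date of documented progression") while scans are scheduled "relative to the date of first dose of study treatment". Timed from enrolment, a gap to first dose of more than 183 − 175 = 8 days could put 6 months before the week-24 scan. Use an exact cut-off: at least 17 of 25 event-free (type I 2.5%, power 48%) or, for 41, at least 25 (4.5%, 78%). Say how a subject without a week-24 scan is counted.

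The cost is wording; no added patients or scans. The downsides should be stated. Power at 25 is well below 80% and depends on curve shape (37% to 59% for the Weibull shapes above). The cut-off of 25 of 41 slightly exceeds 5% at shape 0.8. The test and the descriptive PFS would have different time origins.
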